#### Masking Procedure and Labeling:

In order to preserve the double-masking of the trial, only the investigation pharmacy will be unmasked. Both treatments (NAC and placebo) will be distributed from the investigational pharmacy. Except for the pharmacist, all staff will be blinded to the treatment sequence.

#### PROCESS OF OBTAINING INFORMED CONSENT:

The informed consent process will involve a member of the study team and the parent and child. If the individual is recruited over the telephone or by advertisements/mail/email, he or she will be sent a consent form and be contacted by a study coordinator to review the details of the study and answer questions. Interested families will then undergo screening as described in the *Eligibility Verification* document (a checklist of eligibility criteria).

Prior to study entry, all children recruited will undergo an initial screening lasting up to 15 to 20 minutes with a parent to determine their general suitability for inclusion or exclusion. This screening may be done over several days and can take place in person, on the phone, via email,

#### Randomization:

Following the screening period, each participant will be sequentially assigned to one of the 2 treatment groups: NAC or placebo. This randomization will be stratified to ensure balance of ADHD, ages and sexes between the intervention groups. Randomization will be implemented by the study statistician for this trial utilizing a permuted blocks approach. Password protection will be implemented to ensure that only certified clinical personnel are allowed to randomize patients and access the database. At the time

videoconference, and/or via electronic surveys such as REDCap. If determined to be eligible during the initial screen, the patient will enter the second phase of screening as outlined in the *Eligibility Verification* document.

After eligibility criteria are confirmed, the informed consent process will occur. Informed consent can take place in person, on the phone, via email, videoconference, and/or via electronic surveys such as REDCap. Following the consent process, eligibility screening will occur. The primary diagnostic screen will be the PANESS. Clinically administered PANESS scores performed within 90 days of enrollment can be used to confirm eligibility and as a baseline PANESS score for this study. Participants whom have not had a recent (within 90 days) PANESS assessment as a part of clinical care will be screened with PANESS. A set of behavioral and neuropsychometric assessments will be administered and families will be informed if they are eligible for the next phase of the study. The questionnaires are outlined in **Table 4**.

Parents/participants will deliver a teacher rating scale packet, with questionnaires/rating scales targeted to the classroom environment, to their child's teacher. Teachers will return completed rating scales to the study team via US mail using an addressed/stamped envelope provided by the study team. A letter will be included within the teacher packet indicating that, by completing the questionnaires and mailing them in, they provide implicit consent. Communication with teachers and distribution of surveys may occur digitally via REDCap, telephone, videoconference, and/or email.

#### *NAC/Placebo Treatment*

After initial screening (visit 1) and baseline (visit 2, completed only on initial entry to the study) there will be approximately two on-site study visits (**Table 4**), involving approximately 120 minutes of diagnostic, motor, and neuropsychological assessment, a 90-minute TMS session, and 60 minutes of actual scan time (total = 5-6 hours). The administration of all interviews and cognitive testing will also be standardized with respect to personnel. A third day of testing may be added to accommodate the subjects' schedules and all research evaluations.

#### *Non NAC/Placebo treatment cohort*

These participants will undergo the baseline studies (TMS, MRI, motor testing, cognitive testing), as described in the prior paragraph, but no further on-site visits.

#### Consent

A separate consent form will be signed by each participant. Subjects 11 years and older will provide documented assent via a signature on the consent form.

Participation in this study will not change current medical treatment. Permission of the primary care/attending physician will not be sought.

To minimize the possibility of coercion, families will be encouraged to discuss this study in private (without the presence of study staff) and to ask the study staff questions to ensure understanding

of the study parameters. The decision to enroll can be considered for the duration of the enrollment period (e.g. until recruitment goal is reached).

For minor subjects who are brought to CCHMC by a person other than the parent or Legally Authorized Representative (LAR), the consent form may be sent to the parent for review. If so this consent process can take place over the phone, via email, videoconference, or REDCap eConsent. If the parent or LAR agrees to allow the participant to take part in the study, a copy of the signed consent will be returned and reviewed by a study coordinator before any research procedures occur. The consent form can be returned to CCHMC by fax, e-mail, regular mail, or REDCap eConsent response (which would be documented with a pdf in the participant's e-regulatory folder).

#### **Electronic Consent (e-Consent) and Assessments:**

To securely and efficiently maintain the data collected for this study, an electronic (eREG) binder will be utilized. As described below, paper regulatory documents will be scanned, verified, and filed in the eREG folder. To optimize the eREG process, electronic consent and assessments can be utilized. The format of electronic regulatory documents include pdf and/or REDCap. In addition to facilitating questionnaire distribution and document management, REDCap will enhance data analysis. Digital consent forms and questionnaires can be distributed to the participants/families who have reliable access to internet/email. Completion of electronic questionnaires and/or signing of e-Consent documents may take place during study visits using CCHMC resources (tablet, computer, signature pad) currently available to the study team.

#### **Partial HIPAA Waiver**

To facilitate eligibility screening of potential participants, the study team will implement a partial HIPAA waiver to screen, recruit, or determine eligibility of prospective subjects for a research study without screening-specific informed consent. As such, protected health information (PHI) access/retention for the purposes of identifying potential subjects is allowable. The use or disclosure of protected health information involves no more than a minimal risk to the privacy of individuals undergoing eligibility screening for this study. Eligibility screening for this study will not adversely affect the rights and welfare of the subjects. As with all research participants, security of protected health information (PHI) obtained during eligibility screening will be prioritized as described below.

#### **PARTICIPANT WITHDRAWAL**

A participant may withdraw from the study at any time. Participants considering withdrawal should contact the investigator so that the investigator can help you with a plan to stop the study drug safely.

The person in charge of the research study or the sponsor can remove participants from the research study without their approval. Possible reasons for removal include:

1. Adverse events requiring removal from protocol therapy
2. Inability or refusal to continue the study by patient/parent/guardian
3. Physician determines it is in patient's best interest

In the case of participant withdrawal/removal, data already collected may not be removed from the study database. The study team will request permission to collect data from your routine medical care. If the participant agrees, this data will be handled the same as research data.

The study team will inform the participant about any new information that may affect health, welfare, or choice to stay in the research.

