In the event that a participant is lost to follow-up, an incomplete series of observations can still be analyzed using the mixed-model methodology, provided that the dropout can be assumed to be missing at random in the sense that the probability that data are missing depends only on observed covariates (e.g., prior values of the outcomes, treatment assignment), rather than the unobserved values themselves. This assumption cannot be directly verified from the data. When it holds, however, mixed-model procedures yield the most efficient unbiased estimates, and implicitly impute the missing data using a subject-specific linear trend estimated from the non-missing observations. This effectively assumes that observed trends would have continued, in contrast to the "last observation carried forward" assumption that future observation would remain at a constant level equal to the last value. Neither assumption can be empirically proven correct. As a sensitivity analysis, therefore, the last available observation will be substituted for the protocol-defined last observation, provided that the participant had received at least one dose of study medication prior to the last observation. It is possible to determine whether participants who drop out are systematically different from those who do not with respect to observed data (e.g., baseline values, treatment assignment, demographic and clinical covariates). Logistic regression analyses will be used to explore whether such variables are predictive of dropout.

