**COMPLIANCE AND SAFETY MONITORING:**

Monitoring and Managing Adherence to Treatment:

Pill/Sachet counts and/or review of the medication log will be used to estimate compliance, along with queries about missed doses. We will require a standard of four days out of seven on treatment to obtain a rating but will counsel the participant and family about the importance of adherence in such a situation. We will require a minimum of 5 days per week on treatment in each of the final two weeks of each treatment block, so that the end-of-treatment ratings are an accurate reflection of treatment. For the final study visit and pTMS assessment, subjects must have 100% compliance for the two days prior to testing or testing will be rescheduled within a reasonable 3-4 day window so that compliance can be assured.

Communication:

To facilitate data collection, safety monitoring, and accommodate preferences of participants, communication between study staff and the research participant/family/teachers will utilize a variety of technologies. Modes of communication may include phone calls, videoconference, electronic mail (e-mail), REDCap surveys (via e-mail link or Twilio text message), and in person meetings. Responses to safety assessments will be reviewed by a member of the study team within 48 hours. As described elsewhere, if a participant/family discloses any suicide ideation or significant health concerns at any point in this study, the study staff will contact the participant's mental health provider or primary care provider and/or Psychiatric Intake Response Center (PIRC) at CCHMC for further assessment and guidance within 24 hours.

Video recordings may aide recruitment and explanation of study assessments/details. These recordings may be distributed in a similar manner to other advertisements (websites, philanthropic/educational events, through interactions related to clinic visits, distributed via REDCap correspondence, et cetera). Examples or video content would be a short description of TMS and PANESS procedures. A general outline of the study (risks/benefits, procedures, timeline, et cetera) as would be described during informed consent would also be advantageous.

Medical/safety assessments:

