**Table 8: General Dose Modification Guidelines**

CTCAE Grade	Action and Dose Modification
Grade 1	
 
• Continue treatment at current dose level
 
• Monitor closely
 
• Provide supportive care according to institutional standards
 

Grade 2	
 
• Interrupt treatment if clinically indicated
 
• Monitor closely
 
• Provide supportive care according to institutional standards
 
• When toxicity resolves to grade 1 or baseline, restart treatment at current dose level
 

Grade 3	
 
• Interrupt treatment
 
• Monitor closely
 
• Provide supportive care according to institutional standards
 
• When toxicity resolves to grade 1 or baseline, restart treatment reduced by half
 

Grade 4	
 
• Interrupt treatment
 
• Monitor closely
 
• Provide supportive care according to institutional standards
 

	

• Restart with treatment reduced by half once toxicity resolves to grade 1 or baseline

• If the grade 4 toxicity recurs, permanently discontinue treatment

--	--

The occurrence of adverse events should be sought by non-directive questioning of the patient at each visit during the program. Adverse events also may be detected when they are volunteered by the patient during or between visits or through physical examination, laboratory test, or other assessments. All adverse events must be recorded in an agreed-upon format, such as on the Adverse Event Form, which will be provided with the following information:

1. Severity grade (mild, moderate, severe)
2. Relationship to the drug(s) of interest (suspected/not suspected)
3. Duration (start and end dates or if continuing at final exam)
4. Whether it constitutes a serious adverse event (SAE)

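### The withdrawal section lets a child be removed from the whole study when an adverse event ends study drug, and nothing requires week-8 and week-12 assessments off drug

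*Combined protocol and SAP*

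**What the plan says.** Participant Withdrawal gives a discretionary power: "The person in charge of the research study or the sponsor can remove participants from the research study without their approval". A list follows, introduced by "Possible reasons for removal include", and its first entry is "1. Adverse events requiring removal from protocol therapy". The second entry separately covers a family that cannot or will not continue. On data, the section states "In the case of participant withdrawal/removal, data already collected may not be removed from the study database". For the period after removal it offers only "The study team will request permission to collect data from your routine medical care".

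Table 8 deals with drug actions by toxicity grade. Its only permanent stop is "If the grade 4 toxicity recurs, permanently discontinue treatment". It says nothing about visits.

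Compliance and Safety Monitoring says "We will require a standard of four days out of seven on treatment to obtain a rating". It also asks for at least five days per week on treatment in each of the last two weeks, so that the end-of-treatment rating reflects treatment.

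Table 4 schedules PANESS at baseline, week 8 and week 12 only, and has no early-termination visit. Adverse event assessment continues at weeks 2, 4, 6, 8, 10 and 12, and the C-SSRS at weeks 4, 8, 10 and 12. Vitals, safety labs and physical examination (baseline, weeks 8 and 12) are marked as standard of care.

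On missing data, Statistical analysis says that "an incomplete series of observations can still be analyzed using the mixed-model methodology" if data are missing at random. It adds a last-observation sensitivity analysis, limited to participants dosed before that observation, and a logistic regression of dropout on observed variables.

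**The concern.** An event that concerns the drug is listed as a ground for leaving the study. Children who only refuse or cannot continue are already covered by another entry. The adverse-event entry therefore mainly adds children who might still be willing to attend. Even a child who is not removed has no clear route to a week-8 rating, because the compliance rule asks for days on treatment that an off-drug child cannot supply.

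The primary outcome can then go missing because of how treatment was tolerated. The protocol lists rash, urticaria, diarrhea, nausea and vomiting among the common effects of NAC, so unequal loss between arms is plausible, though not shown. A comparison of the children who remain would describe those who tolerated their assigned treatment, not all who were randomised. Safety and tolerability is also a secondary aim, and the children with the worst reactions could miss the later scheduled C-SSRS and adverse event assessments.

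**Working it through.** **The plan's own figures.** Determination of sample size gives 26 per group, effect size 0.8, a two-sided t-test at 0.05, and 81% power. The noncentral-t calculation gives 80.7%. With 10% dropout, 52 / 0.9 = 57.8, so 58 are enrolled, 29 per arm. Both figures reproduce, and the point does not turn on them.

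**What is observed for a child who stops before week 8 and is removed.**
- PANESS: the baseline value only.
- Mixed model: the plan describes implicit imputation from a subject-specific linear trend. One pre-treatment value gives no trend. The model can only predict the child's week-8 score from the baseline and from other children in the arm, in effect as if the child had followed the arm's retained members.
- Last-observation analysis: read literally, the dosing condition excludes the child, because the only PANESS precedes the first dose. If baseline were carried forward anyway, the change would be set to zero by construction. Neither result is information about the child's outcome.
- Missing at random: the examples given are prior outcomes and treatment assignment. The list is open, so an adverse event could be added, but the plan does not name it as a variable in the outcome model.

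**Size, illustration A.** Inputs: 29 NAC children and the design effect of 0.8 SD. Assumptions: retained children have the full 0.8 SD, children who stop have no effect, and k NAC children are lost.

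Effect in all randomised = 0.8 × (29 − k)/29. Excess of the retained-children estimate = 0.8 × k/29.

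| k | Excess (SD) | Share of design effect (k/29) |
|---|---|---|
| 2 | 0.8 × 2/29 = 0.06 | 7% |
| 3 | 0.8 × 3/29 = 0.08 | 10% |
| 4 | 0.8 × 4/29 = 0.11 | 14% |
| 6 | 0.8 × 6/29 = 0.17 | 21% |

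Placebo losses do not alter these values if placebo PANESS does not change, as the sample size section assumes.

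**Size, illustration B.** Suppose the lost children would have changed by D SD less favourably than those retained. The retained NAC mean is then shifted by (k/29) × D: from 2/29 × 0.5 = 0.03 SD to 6/29 × 1.0 = 0.21 SD. Equal selection in placebo would offset this, so here k is the excess of NAC over placebo losses.

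**Power.** If 1 to 6 NAC children are lost beyond the planned 3 per arm, power at 0.8 falls from 80.7% to between 79.9% and 74.9%. That loss is modest. Selection is the larger issue.

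**The case against.** The strongest reply is that the text is permissive. The study lead or sponsor may remove a child and need not, so a child off drug could be kept in follow-up. That stands. A reader might infer that every adverse-event discontinuation takes the child out of the study, but the documents do not say so.

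A reader might also infer that Table 8 contradicts the withdrawal section. It does not: it governs drug actions and is silent on attendance. Most of its rows lead to continuing or restarting, and only a recurrent grade 4 toxicity ends treatment for good. Removal after an ordinary episode of rash or vomiting is therefore not the table's default course.

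Nor would all safety information be lost. Earlier data stay in the database, the adverse event itself is recorded, and labs, vitals and examinations are marked standard of care and might be obtained with permission. PANESS is sometimes done in clinical care, as the eligibility text acknowledges, but nothing secures one at week 8.

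The size is also uncertain. The 10% dropout allowance (about 6 of 58) is all-cause and covers both arms, so it does not support k = 6 in NAC. An even split is about 3 per arm, or 0.08 SD. The standard error of the difference with 26 per arm is √(2/26) = 0.28 SD, so even 0.17 SD is below one standard error. Calling the excess an overstatement also presupposes that the target is the effect in all randomised children, which the plan does not state.

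What remains is that two stated rules, on removal and on rating, both point toward losing these outcomes, and no rule points the other way.

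**Conclusion.** The point holds as a gap that permits selective loss. The plan allows removal from the study when an adverse event ends treatment, ties ratings to being on drug, and nowhere requires week-8 or week-12 assessment off drug. A child who stops before week 8 can have only a baseline PANESS, and the planned analyses cannot recover that child's outcome. Scheduled C-SSRS and adverse event assessments can also be missed.

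Under illustration A the excess is 0.06 to 0.17 SD for 2 to 6 NAC losses, against a design effect of 0.8 SD. These values rest on an assumed number of losses, no effect after stopping, and an all-randomised target. The documents supply no discontinuation rate, so they do not show that NAC losses will exceed placebo losses or that the bias will be large. No change to the sample size follows. The case for acting is that outcomes not collected cannot be recovered later and the visits are already in the schedule.

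**What to change.** 1. In Participant Withdrawal, separate stopping study drug from leaving the study. List adverse events that end therapy as a reason for stopping drug only.
2. State that children who stop drug continue the scheduled week-8 and week-12 PANESS, questionnaires and safety assessments unless the family declines.
3. Record the date and reason for stopping drug separately from the date and reason for leaving the study.
4. Reconcile the on-treatment rating requirement in Compliance and Safety Monitoring with this, so that off-drug children are still rated and flagged as off drug. Amending the withdrawal section alone would leave them without a rating.
5. In Statistical analysis, include their week-8 PANESS in the NAC–placebo comparison in the arm to which they were randomised. Keep an on-treatment analysis as supportive.

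Clinical stopping and dose rules are unchanged.

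Cost: minor amendments to the withdrawal and compliance sections, a sentence in the analysis section, extra form fields, and some visits by children who are off drug. The estimated effect may be somewhat smaller than among children who stayed on treatment.

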## **STUDY PROCEDURES:**

### **Study Variables and Measurements - Overview:**

We propose to study all measurements at baseline, 8 weeks after treatment, and 4-week post-treatment (washout period) to assess for carry-over effects. We will compare PANESS and SICI measures in 58 children with NF1 to data already acquired at CCHMC for those 2 measures (**Figure 14**). Next, these children will be treated with NAC (n=29) or placebo (n=29) as described above (**Figure 16**).

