**BACKGROUND:**

***Neurofibromatosis type 1 (NF1)***

Neurofibromatosis (NF1) is an autosomal dominant condition affecting many organs, resulting from mutations in the neurofibromin 1 gene [1]. Characteristically, individuals with this condition have cutaneous manifestations, most prominently hyperpigmented macules termed “café-au-lait” spots. The neurofibromin gene functions in part as a tumor suppressor, and persons with NF1 are susceptible to malignant and benign tumors in multiple organs. What is less well studied is that individuals with NF1 commonly suffer from difficulties with behavioral and emotional regulation including attention-deficit/hyperactivity disorder (ADHD) symptoms, learning disabilities, and developmental delays in motor function [2]. These cause substantial morbidity in childhood and throughout life. There are no effective treatments for motor behavior and/or learning difficulties for NF1 and other RASopathies. Lack of sensitive objective biomarkers that can evaluate motor system or behavioral symptoms causes difficulties in evaluating the efficacy of pharmacological interventions in NF1.

*Preliminary results regarding motor function and brain-based measures as a rationale for additional study.* A pre-planned analysis of predictor variables for NAC response has been performed, prior to breaking the blind in the randomized controlled treatment study. We performed these analyses on measures obtained at the baseline (pre-treatment) visit. These findings are now published, and some additional findings will be presented at scientific meetings. The strength of these preliminary findings warrants an expansion of the secondary aims, in order to validate these measures in a larger sample. Inclusion/exclusion criteria will be minimally changed to expand eligibility without compromising safety or study rigor. Individuals not wishing to participate in the NAC vs. Placebo treatment may elect to enroll and participate in an assessment of the baseline biomarkers. This will allow for additional assessment of the relationship between these measures and the NF1 diagnosis as well as for associations with motor and cognitive/behavioral impairments.

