**SELECTION AND RECRUITMENT OF PARTICIPANTS:**

We plan to enroll 58 children ages 8-16 years with NF1 (**Figure 16**). Recruitment will be primarily from the NF1 and RASopathies Programs at CCHMC. The multidisciplinary program at CCHMC follows over 1500 individuals with NF1 and over 60% are under 20 years of age. We will also recruit from local events (including philanthropic and education events). Advertisements may also be posted on the NF1-associated websites including, but not limited to the Children's Tumor Foundation (CTF) website, NF1 facebook group, RASopathy facebook group, et cetera. Physical presence of research personnel in the clinic has been minimized in response to the covid-19 pandemic. Video recordings may aide recruitment and explanation of study assessments/details. These recordings may be distributed in a similar manner to other advertisements (NF1-associated websites, philanthropic/educational events, through interactions related to clinic visits, et cetera). Examples or video content would be a short description of TMS and PANESS procedures. A general outline of the study (risks/benefits, procedures, timeline, et cetera) as would be described during informed consent would also be advantageous.

An additional “Single visit, non-treatment” cohort will be recruited of 40 individuals with NF1 for a single “biomarker” study visit. These individuals will undergo motor function (PANESS) and brain-based measures (TMS, MRI-MRS, MRI-DTI) as biomarkers of impaired executive function (ADHD-RS; BRIEF-2; TOVA), but will not be assigned to receive NAC/Placebo.

We will use control data from age matched children ages 8-16 years, from previous studies (cohorts of 52 children with ADHD and 62 typically developing children).

We will also use advertising materials approved through the CCHMC Institutional Review Board (IRB). These include emails and small flyers which are posted at CCHMC locations. The study will be posted in clinicaltrials.gov.

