**Inclusion criteria :**

1. Male and females aged 8 - 16 years (up to 16 years and 6 months) at time of enrollment
2. Meets NIH diagnostic criteria for NF1
3. Abnormal PANESS study (score at or above the age/sex-based mean)
4. Participants must have a full-scale intelligence quotient (IQ) of 70 or above, as determined by neurocognitive testing within the last 3 years or during the enrollment process
5. Participants on stimulant or any other psychotropic medication should stay on a stable dose (no change in dose) for at least 30 days before entering the study. A stable dose should be maintained throughout the study until completion of all study visits.

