### **Psychometric Measures**

All primary measures will first be administered at screening. ***We will use the Response Evaluation in Neurofibromatosis and Schwannomatosis (REiNS) Neurocognitive committee reviewed and recommended assessment tools to assess symptomatology in NF1.*** The length of time required for the child to complete the baseline neuropsychological assessment is estimated to be approximately 90 minutes, including self-report questionnaires. Parent questionnaires can be completed simultaneously while the child is being evaluated and can be completed in about 30

minutes. All neuropsychological assessments that will be used in this study are published tests that have normative data and established reliability and validity for the age range in this study. These tests are all extensively used in clinical and/or research settings. All tests have standardized instructions for administration ensuring there will be no site variation in administration.

To minimize any test-retest effects for neuropsychological outcome measures, alternate forms will be used where possible, to minimize potential practice effects. Furthermore, the use of a placebo group will allow us to identify any potential practice effects and distinguish whether any changes in the treatment group are larger than those accounted by practice effects. In addition, statistical analysis of the data will be conducted to account for confounding variables such as practice effects.

The WISC-V testing is optional for individuals who will not be receiving NAC/Placebo. However, the PANESS and the neuropsychometric testing below will be performed in all “single-visit, non-treatment” participants.

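### Minor: the entry criterion truncates baseline PANESS in the 58 randomised NF1 children, so comparing them with existing CCHMC data overstates the NF1 motor deficit; the NAC-placebo contrast is unaffected

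*Combined protocol and SAP*

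**What the plan says.** - **The comparison.** *Study Variables and Measurements - Overview*: "We will compare PANESS and SICI measures in 58 children with NF1 to data already acquired at CCHMC for those 2 measures". The next sentence says that these children then receive NAC (29) or placebo (29), so the 58 compared are the 58 randomised.
- **The entry rule.** *Inclusion criteria*, item 3: "Abnormal PANESS study (score at or above the age/sex-based mean"). The reference population for that mean is not stated.
- **The likely comparison groups.** *Selection and Recruitment of Participants* plans to use existing data from "cohorts of 52 children with ADHD and 62 typically developing children". No PANESS cut-off is given for them. The overview cites Figure 14, which is not shown, so the link to these cohorts is an inference.
- **Which score is the baseline.** The screening text under *Randomization* says that a clinical PANESS from the previous 90 days "can be used to confirm eligibility and as a baseline PANESS score for this study". *Psychometric Measures* says "All primary measures will first be administered at screening", while Table 4 lists PANESS at Visit 2 and not at Visit 1. Some children may thus have a reused score and others a new one.
- **The second NF1 cohort.** Forty children will have a single visit without treatment. *Psychometric Measures*: "However, the PANESS and the neuropsychometric testing below will be performed in all" of them.
- **The analysis text.** *Data Analysis/Methods* neither mentions this comparison nor labels or corrects for the selection.

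**The concern.** PANESS is both the variable that decides who enters the NF1 group and the variable on which that group is compared. A higher score is worse, since *Determination of sample size* counts a decrease as improvement. Removing the low scorers from one side only raises the NF1 mean and widens the apparent gap.

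This matters because the documents want to say something about NF1 itself. *Purpose of Study* seeks biomarkers related to the presence of NF1, and *Background* seeks the relation of these measures to the diagnosis. A reader of a report would take the result as NF1 versus controls, whereas it describes only NF1 children at or above the age/sex mean. The same upward shift enters a comparison with the ADHD cohort. SICI is not selected on directly and moves only through its correlation with PANESS.

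**Working it through.** **The plan's own figure.** The documents give no figure for this comparison. The only related calculation is the trial sample size, and it reproduces: 26 per group, d = 0.8, two-sided 0.05 gives t-test power 0.807 (stated: 81%), and 52/0.9 = 57.8, so 58. Nothing below changes it.

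**Inputs.** From the documents: 58 NF1 children, 62 typically developing, 52 ADHD, 40 non-treatment, and a lower cut at the age/sex mean. Not in the documents, hence assumed: normal scores, control SD 1, cut at the control mean, true gap g from 0.5 to 2.0 SD, NF1 SD s of 1 or 1.3, and PANESS retest correlation r from 0.6 to 0.9. The documents give retest figures for other instruments but not for PANESS.

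**Formula.** Excess in the NF1 mean when the qualifying score is the analysed score: s·φ(g/s)/Φ(g/s). Share of NF1 children eligible: Φ(g/s). If PANESS is re-measured after screening, multiply the excess by r.

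Example at g = 1.0, s = 1: 0.242/0.841 = 0.288, so the expected observed gap is 1.29 instead of 1.00.

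| True gap (SD) | Eligible, s = 1 | Excess, s = 1, reused | Observed gap | Excess, s = 1, re-measured (r 0.6 to 0.9) | Excess, s = 1.3, reused |
|---|---|---|---|---|---|
| 0.5 | 69% | 0.51 | 1.01 | 0.31 to 0.46 | 0.74 |
| 1.0 | 84% | 0.29 | 1.29 | 0.17 to 0.26 | 0.50 |
| 1.5 | 93% | 0.14 | 1.64 | 0.08 to 0.12 | 0.30 |
| 2.0 | 98% | 0.06 | 2.06 | 0.03 to 0.05 | 0.17 |

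**If the reference mean is not the control mean.** With the cut 0.5 SD below or above the control mean (s = 1, reused score), the excess is 0.14 or 0.51 SD at g = 1.0, and 0.02 or 0.14 SD at g = 2.0. The size changes; the sign does not.

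**SICI.** Shift = correlation × excess. At g = 1.0 this is 0.03, 0.09 or 0.14 SD for assumed correlations of 0.1, 0.3 or 0.5.

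**Does adding the 40 suffice?** Not if the screen failures are left out. With an unselected 40, the pooled bias at g = 1.0 is 58 × 0.288/98 = 0.17 SD (0.08 at 1.5, 0.03 at 2.0). If all screened children are kept, the truncation term is zero.

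**Residual bias from losses before consent.** Suppose half of those below the cut are removed before consent. At g = 1.0 those below the cut average 1.525 SD under the NF1 mean, so the bias is (0.841 × 0.288 − 0.079 × 1.525)/(0.841 + 0.079) = 0.13 SD. At 1.5 and 2.0 it is 0.07 and 0.03.

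**The case against.** The strongest reply is that this is peripheral. The comparison is one sentence in an overview. It is neither the primary nor a secondary aim, and it has no test, hypothesis or power calculation. The entry cut is openly stated. At true gaps of 1 to 2 SD with equal SD, the excess (0.06 to 0.29 SD) lies inside the 95% half-width for 58 versus 62, 1.96 × √(1/58 + 1/62) = 0.36 SD, and the conclusion that a deficit exists would not change. All of this stands, and it is why the point is minor. It does not remove the bias: sampling error averages out over studies and truncation does not, and the estimated size of the deficit would be quoted.

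A second reply is that a remedy is already in the plan. The note on the ψ mark opens by saying that it covers inclusion and exclusion criteria for both cohorts. Criterion 3 carries no mark, which suggests that it binds the treatment cohort only. That is the likelier reading, but it is not settled: the NF1 diagnosis item is unmarked too, and the note describes unmarked items only as exclusion requirements. Nor does the plan assign the 40 to this comparison.

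Three stronger readings are tempting and not supported:
- **That the treatment effect is biased.** Both arms pass the same cut before randomisation.
- **That the comparison would manufacture a deficit.** With no true gap and a reused score the excess is 0.80 SD, and 58 versus 62 is almost always significant. But the PANESS section reports preliminary data suggesting a real deficit.
- **That the deficit is known to be large, so the bias is negligible.** The same section says only that problems may be more extreme and gives no size.

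**Conclusion.** The point holds as a minor one. Followed as written, the plan compares a PANESS-truncated NF1 group with cohorts for which no such truncation is stated, and so overstates the NF1 motor deficit. The direction is certain unless no NF1 child scores below the age/sex mean. The size cannot be fixed from the documents. With a reused score and a cut at the control mean, it runs from 0.51 SD at a true gap of 0.5 SD to 0.06 SD at 2.0 SD with equal SD, and is higher if NF1 scores are more variable. Re-measurement reduces it without removing it. These figures rest on normality and on assumed gaps, SDs and retest correlations. That the comparators are the typically developing and ADHD cohorts is probable but inferred. What is affected is what may be reported about NF1 versus controls on PANESS and, to a lesser degree, on SICI.

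**What to change.** 1. In *Study Variables and Measurements - Overview* and in *Statistical analysis*, state that the 58-child PANESS comparison describes NF1 children at or above the age/sex mean and supports no inference about NF1 as a whole.
2. Base any PANESS inference about NF1 versus controls on NF1 children not selected on PANESS: all consented children with a score, including those who fail criterion 3, plus the non-treatment cohort, each child counted once. State under *Inclusion criteria* that criterion 3 does not bind the non-treatment cohort.

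**Cost.** A few sentences and no new visits. The protocol places the screen after consent ("Following the consent process, eligibility screening will occur. The primary diagnostic screen will be the PANESS"), so scores of screen failures will exist, and PANESS is already planned for the 40. With s = 1 and true gaps of 1.0 to 2.0 SD, 58 eligible children imply about 69 to 59 screened (58/0.841 to 58/0.977). That gives about 109 to 99 NF1 children with the 40 added, if no failure moves into that cohort. Against 62 controls the gap detectable with 80% power is then about 0.45 to 0.46 SD, compared with 0.57 SD for the 40 alone.

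**Downsides to state.**
- Scores of ineligible children must be kept.
- Eligibility screening before consent is allowed (*Partial HIPAA Waiver*), so low scorers removed then stay missing and some upward bias may remain.
- The cohorts differ. The asthma, psychiatric and MEK-inhibitor exclusions, among others, are unmarked and so bind only the treatment cohort. The non-treatment cohort also includes volunteers who declined treatment ("Individuals not wishing to participate in the NAC vs. Placebo treatment may elect to enroll and participate in an assessment of the baseline biomarkers"). Results should therefore also be shown by cohort.
- *Background* says that a baseline analysis is already published, and that cannot be changed. The documents do not say whether it used controls.
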